**Objectives**

The purpose of this randomized, double blinded, prospective study is to compare the postoperative analgesia provided by the PENG block to that provided by the LPB for patients undergoing primary anterior approach THA. We hypothesize that the PENG block will provide equivalent analgesia to LPB after THA. The primary outcome will be a comparison of patient-reported numeric rating scale (NRS) pain scores with movement at six hours following block placement. Equivalency will be defined as a difference of less than one point in either direction on the eleven-point NRS pain scale (0-10). Secondary outcomes will include NRS pain scores with movement at 12, 18, and 24 hours, NRS pain scores at rest at 6, 12, 18, and 24 hours, time to first opioid administration, cumulative dose of postoperative opioid administration within the first 24 hours, motor strength at six hours after block placement as assessed by straight leg raise on a six-point scale (0-5), and distance walked at first postoperative physical therapy session. The 18 hour assessment for pain at rest and with movement is allowed to be done retrospectively at the time of the 24 hour assessment, as this time point would end up interrupting the sleep of the study subject as would be occurring in the early morning hours. If the subject reports asleep

at the 18 hour scheduled time point, the no pain score will be obtained. This will be considered a missing data point and not a deviation. If the subject reports they were awake at the 18 hour time point, then a pain score at rest will be obtained but if the subject reports no movement, this score will be a missing data point and not a deviation.

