### **Interventions**

Once randomization occurs, standard American Society of Anesthesiology (ASA) monitors and supplemental oxygen will be applied to the patient, and a timeout procedure will be conducted to verify all patient data and paperwork are correct. Unless the patient has a contraindication, each patient will also receive a weight-appropriate dose of acetaminophen and celecoxib, or meloxicam (if the patient has an allergy to sulfonamide medications or to celecoxib) at this time.

All blocks will be performed by an experienced faculty anesthesiologist well versed in the performance of LPB and PENG blocks, or by a regional anesthesia fellow directly supervised by a regional anesthesia specialized faculty anesthesiologist. Sedation for block placement will be administered using midazolam and fentanyl titrated to patient comfort, at the discretion of the attending anesthesiologist performing or supervising the regional anesthesia procedures. All subjects will start in the supine position, and their relevant anatomy for PENG block will be imaged using an ultrasound as described previously, after skin preparation with chlorhexidine solution. All subjects will then receive a skin wheal using 1mL of 1% lidocaine at the skin entry site for a typical PENG block. Those subjects assigned to the PENG treatment arm will subsequently receive a PENG block using 20mL of 0.2% ropivacaine with 1:400,000 epinephrine dosed in 5mL increments with negative aspiration beforehand and between each aliquot. All subjects will then be transitioned to lateral decubitus positioning with the surgical

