side up (standard at our institution, as we use an isobaric spinal solution). Using a skin marker, midline will be marked on their lumbar spine at the level of the iliac crests, and a point two thirds the distance between midline and the posterior superior iliac spine on the surgical side will be marked. Following this, their lower back areas will be prepared with antiseptic solution and draped in sterile fashion. All subjects will then receive a skin wheal with 1cc of 1% lidocaine at the standard LPB block site just marked as described above. Those subjects assigned to the LPB treatment arm will subsequently receive a stimulation-based LPB dosed with 20cc of 0.2% ropivacaine with 1:400,000 dilution epinephrine dosed in 5mL increments with negative aspiration beforehand and between each aliquot. The PENG block site skin wheal will behave as a sham block for subjects enrolled in the LPB arm, and the LPB block site skin wheal will behave as a sham block for those enrolled in the PENG arm.

All patients will then receive a spinal block as the primary anesthetic using 3.5mL of 0.5% ropivacaine with 10mcg fentanyl. Following placement of the spinal block, the patients will be brought to the operating room and receive our standard intraoperative protocol of propofol infusion for sedation, along with dexamethasone 10mg IV, ondansetron 4mg IV, surgical antibiotic prophylaxis as appropriate, and IV tranexamic acid 1g at both capsule opening and capsule closure. Any patients whose spinal block are determined to have failed, as checked prior to initiation of propofol sedation and surgical skin preparation with a pinch test on the surgical lower extremity, will be induced under general anesthesia using propofol with placement of a laryngeal mask airway or endotracheal tube at the discretion of the attending anesthesiologist.

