## Measurements

Following the completion of surgery, all subjects will be brought to the post-anesthesia care unit (PACU) for recovery, where they will recover until satisfactory resolution of spinal block as judged by an attending anesthesiologist is shown. Subjects will then be transported to an inpatient room, where nurses will monitor their vital signs and pain scores regularly. Subjects will receive standard of care pain medications for postoperative pain management as indicated. Subjects will continue to receive scheduled acetaminophen 1000mg every six hours (or 15mg/kg if their weight is below 65kg), and the NSAID administered preoperatively (either celecoxib 200mg twice daily or meloxicam 15mg once daily) barring any contraindication such as renal impairment or vascular disease. Oxycodone every four hours may also be administered as needed with dose ranges determined by the Davie Medical Center perioperative surgical home anesthesiologist consulted for postoperative care, or another narcotic at equipotent dosages if they have a contraindication to oxycodone. Alternatively, they may receive combination products such as Percocet (oxycodone/acetaminophen) or Vicodin/Norco (hydrocodone/acetaminophen) instead, with the acetaminophen dosage adjusted accordingly. All

opioids will be converted to oxycodone equivalents to allow for appropriate comparison using a widely available dose conversion table.

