Nurses will chart vital signs and medication administration in the electronic medical record (EMR) as per our standard protocol. Research personnel will measure patient-reported NRS pain scores at rest and with movement for each time by patient interaction, either face to face, or by calling the patient's room or phone numbers. This will include the primary outcome of patient-rated pain with movement of the surgical extremity on the NRS pain scale at six hours after block placement (roughly correlating to two hours after arrival to their room) as well as secondary outcomes that include but are not limited to pain at rest and with movement at 12, 18, and 24 hours following block placement, and strength to straight leg raise at six hours post-block placement. The cumulative 24 hour opioid consumption will be abstracted from the EMR for doses received while admitted, and documented by the patient in their pain journal and abstracted via phone call after their discharge, if this occurs prior to 24 hours after the block. Physical therapists will also document their encounters in the EMR, including but not limited to the secondary outcome of distance ambulated during their first session in feet. These metrics will be accessed, abstracted, de-identified, and analyzed by research personnel who are blinded to group allocation.

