### **Data Analysis**

Demographic information will be collected and compared between the groups to verify that randomization balanced out important baseline variables between LPB and PENG. For the primary outcome of patient-reported pain with movement at six hours after block placement, the equivalence hypothesis test of LPB versus PENG groups will be performed using two one-sided t-tests. We will also calculate a point and confidence interval estimate of the difference between LPB and PENG groups. Secondary outcomes will also be compared using t-tests and confidence intervals.

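### Time to first opioid is assigned a t-test, with no rule for a patient who takes no opioid

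*Combined protocol and SAP*

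**What the plan says.** Objectives lists, among the secondary outcomes, "time to first opioid administration, cumulative dose of postoperative opioid administration within the first 24 hours". The 24 h limit is attached to the cumulative dose. Time to first opioid has no stated origin, no end of window and no value for a patient who takes none.

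Data Analysis then covers all secondary outcomes in one sentence: "Secondary outcomes will also be compared using t-tests and confidence intervals". It makes no exception for a time-to-event outcome.

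Measurements makes opioid use discretionary: "Oxycodone every four hours may also be administered as needed", on top of scheduled acetaminophen and an NSAID. On collection it says "The cumulative 24 hour opioid consumption will be abstracted from the EMR for doses received while admitted", with the journal and a phone call covering patients discharged before 24 h. The 24 h window for time to first opioid is therefore inferred from the window for cumulative dose.

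Missing Data Points offers a mixed model, but only for the repeated measurements at 6, 12, 18 and 24 h. The rule in Objectives for a patient asleep at 18 h concerns pain scores only. Censoring and an assigned value are mentioned nowhere.

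**The concern.** A t-test needs a number for every patient. A patient who has taken no opioid by 24 h has none; all that is known is that the time exceeds 24 h. If the field is left blank, the patient leaves the analysis, and the patients removed are those whose analgesia lasted longest. The comparison then describes only patients who took opioid, which is a post-randomisation subgroup defined by the outcome itself.

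Another analyst could assign 24 h to the same patients and report a materially different estimate. Both would comply with the plan. At stake are bias and lost power in one secondary comparison, and a result that depends on a choice nobody wrote down.

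**Working it through.** **The plan's own figure.** The only sample-size figure is for the primary outcome. With SD 2.0, margin 1, one-sided 0.05 for each test, 80% power and a true difference of 0: n = 2 × 2.0² × (1.645 + 1.282)² / 1² = 68.51, rounded up to 69 per arm. This reproduces the plan and does not depend on the present point.

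**When dropping understates the difference.** Let p be the opioid-free share at 24 h and m the mean time among takers, with arm 2 the longer-lasting arm. With 24 h assigned, an arm's mean is (1 − p)m + 24p = m + p(24 − m). So:

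- difference if dropped = m2 − m1
- difference to 24 h = (m2 − m1) + [p2(24 − m2) − p1(24 − m1)]

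Dropping understates the difference when p2(24 − m2) > p1(24 − m1).

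**Inputs for the size.** From the plan: 69 per arm, 24 h, and a 4 h lag before postoperative opioid, because the six-hour assessment is described as "roughly correlating to two hours after arrival to their room" (6 − 2 = 4). Assumed: the shares, exponential times after the lag, and a hazard ratio of 0.6.

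**Worked case, p1 = 5%.**

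- Rates: λ1 = −ln(0.05)/20 = 0.1498 per h; λ2 = 0.6 × λ1 = 0.0899 per h; p2 = 0.05^0.6 = 16.6%.
- Mean time after the lag, restricted to 24 h, (1 − p)/λ: 6.34 h and 9.28 h. Difference 2.94 h.
- Takers only, 1/λ − 20p/(1 − p): 6.676 − 1.053 = 5.623 h and 11.127 − 3.973 = 7.154 h. Difference 1.53 h.
- Check with the condition (adding the lag, m1 = 9.62 and m2 = 11.15): 0.1657 × 12.85 = 2.13 against 0.05 × 14.38 = 0.72. The gap of 1.41 h equals 2.94 − 1.53.

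**All fixed-ratio cases.** Hours are analytic. Power comes from 4,000 simulated trials per row (Welch t-test, two-sided 0.05, complete follow-up; simulation standard error at most 0.8 points).

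| Assumed opioid-free, arm 1 / arm 2 | True difference to 24 h | If dropped | Power, dropped | Power, 24 h assigned | Power, restricted mean | Power, log-rank |
|---|---|---|---|---|---|---|
| 0.1% / 1.6% | 1.86 h | 1.63 h | 78.4% | 83.9% | 84.5% | 84.3% |
| 1% / 6.3% | 2.48 h | 1.75 h | 62.0% | 81.2% | 82.2% | 82.4% |
| 5% / 16.6% | 2.94 h | 1.53 h | 38.1% | 79.4% | 80.1% | 82.1% |
| 10% / 25.1% | 3.02 h | 1.30 h | 23.8% | 73.4% | 74.2% | 76.9% |
| 20% / 38.1% | 2.88 h | 0.99 h | 13.3% | 65.0% | 66.1% | 71.4% |

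With shares held fixed, a shorter lag leaves power unchanged and multiplies the hours by (24 − lag)/20. With no lag, 2.94 h and 1.53 h become 3.53 h and 1.84 h. A separate run with 80 per arm, no lag and other share pairs agrees in direction: at 10%/20%, 1.16 h dropped against 2.55 h assigned, with power 19% against 52%.

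**Bounding cases.**

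- Shares differ only (5%/17%, same timing among takers): 1.85 h true, 0.00 h dropped; power 5% dropped against 42% assigned.
- Timing differs only (5%/5%, takers' means 8.63 h and 10.21 h including the lag): dropped 10.21 − 8.63 = 1.58 h; true 0.95 × 1.58 = 1.50 h. Dropping slightly inflates the difference and has more power (49% against 35% assigned and 36% restricted mean).
- Same takers, shares 20%/22%: 0.22 × 13.79 = 3.03 against 0.20 × 15.37 = 3.07, so the true value is 1.58 − 0.04 = 1.54 h and dropping again inflates slightly.
- No true difference: every method rejects in 4.9% to 5.9% of trials.

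**The case against.** The strongest reply is that the harm needs three things together: a material opioid-free share, shares that differ between arms, and an analyst who drops these patients. The documents establish none of them, and Data Analysis does not say to drop anyone. Measurements also has the analysis done by staff blinded to allocation. This stands as a limit on the size of the problem. Blinding reduces the room for selective choice, but it does not remove the bias if patients are dropped.

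A second reply is that the t-test is not itself at fault. That is largely right. With 24 h assigned and complete follow-up, it is a valid comparison of mean time restricted to 24 h and is within about 1 point of power of the restricted-mean test. The main defect is the missing rule.

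Three stronger readings are tempting and should not be drawn:

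- **That dropping always shrinks the difference when the longer-lasting arm has more opioid-free patients.** The 20%/22% case shows otherwise.
- **That shrinkage helps the trial reach its hypothesis**, "We hypothesize that the PENG block will provide equivalent analgesia to LPB after THA". Equivalence is defined as one NRS point, and the two one-sided tests are named only for movement pain at six hours. Time to first opioid has no margin, and a non-significant t-test would not establish equivalence.
- **That the first opioid is the perioperative fentanyl.** Interventions says "Sedation for block placement will be administered using midazolam and fentanyl titrated to patient comfort" and "All patients will then receive a spinal block as the primary anesthetic using 3.5mL of 0.5% ropivacaine with 10mcg fentanyl", so the literal wording would put the event before surgery in every patient. The stated aim is postoperative analgesia, so postoperative use is the likely meaning. It only needs to be written down.

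**Conclusion.** The point holds as a gap in the plan for one secondary outcome. The plan assigns a t-test to a time that may be unobserved and gives no rule for that case. Analysing observed times only would condition on the outcome. It would understate the difference whenever p2(24 − m2) > p1(24 − m1), as when the longer-lasting arm has clearly more opioid-free patients.

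The size rests on assumed shares, exponential times and a hazard ratio of 0.6. It runs from about 6 points of power at near-zero shares, through 19 points at 1%/6%, to 41 points at 5%/17%, where about half of the difference is lost. With equal or nearly equal shares there is no shrinkage. The primary analysis, the 69 per arm and type I error do not change. It should be fixed before analysis because the remedy is a few sentences.

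**What to change.** For this outcome only, replace the t-test on observed times with wording such as:

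> Time from block placement to first postoperative opioid will be summarised by Kaplan-Meier curves. Patients with no opioid are censored at 24 h, or at last contact if earlier, assuming that loss of contact is uninformative. The arms will be compared by the difference in restricted mean time to 24 h with its 95% CI; a log-rank p-value is supportive. The number of opioid-free patients will be reported per arm.

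The estimate stays in hours. The minimum acceptable alternative is to keep the t-test, state the same origin and window, and assign 24 h to opioid-free patients. With complete follow-up this gives the same estimate.

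**Cost.**

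- SAP wording, and at most one data field: the clock time of the first post-discharge opioid, in the journal or phone call, if not already captured. In-hospital administration is already charted.
- Against log-rank, the restricted mean gives up at most about 5 points of power under the proportional hazards cases above. It gains about 3 to 19 points when the effect wears off (hazard ratio 0.45 to 12 h, then 1; arm 1 shares of 1% to 20%).
- Against dropping, it has less power when the arms differ only in timing among takers (36% against 49%).

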### **Missing Data Points**

If we find that study participants are missing substantial parts of their sequence of longitudinal measurements (6, 12, 18, and 24 hours), we will employ a mixed effects modeling framework that allows us to use all available data to test hypotheses about differences between PENG and

LRB at each time point. Models will be implemented using the ‘lme4’ package in R statistical software.

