## **Statistical Analysis**

### **Power Analysis**

We define an equivalent mean pain score to be a margin of one point in either direction on the eleven-point NRS scale. Based on retrospective quality improvement data at our institution, the patient-reported surgical site pain on the eleven point NRS scale following THA in patients who received a preoperative LPB at Davie Medical Center had a mean of 4.8 and standard deviation of 2.0. Using these values, and setting the significance level to 0.05 with a power of 80%, we calculated the minimum required sample size to be  $n=69$  in the LPB group and  $n=69$  in the PENG group to conclude equivalence of movement pain at six hours between the two groups. Power was calculated using the R package 'TOSTER'. We intend to recruit  $n=80$  patients per arm to allow for attrition and dropout.

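### The secondary pain scores should always be analysed with a baseline-adjusted mixed model, not by t-tests with a mixed model held back for undefined missingness

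*Combined protocol and SAP*

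**What the plan says.** **Primary endpoint.** For movement pain at 6 h, Data Analysis states that "the equivalence hypothesis test of LPB versus PENG groups will be performed using two one-sided t-tests". This is not conditional on anything.

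**Secondary endpoints.** The same section says: "Secondary outcomes will also be compared using t-tests and confidence intervals". No covariate is named. The Objectives section lists seven secondary NRS endpoints: movement at 12, 18 and 24 h, and rest at 6, 12, 18 and 24 h.

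**Missing data.** If participants are found to lack *substantial* parts of the 6, 12, 18 and 24 h sequence, the Missing Data Points section brings in a "mixed effects modeling framework that allows us to use all available data to test hypotheses about differences between PENG and" LPB (printed there as LRB) at each time, fitted with lme4. No threshold is given.

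**Expected gaps at 18 h.** The Objectives section allows the 18 h score to be taken retrospectively at 24 h. A patient who was asleep has no score at all, and one who was awake but did not move has no movement score. Both count as missing data, not as deviations.

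**Baseline.** The Baseline data collection section records NRS at rest and with movement before the block. The analysis sections do not use these as covariates.

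**The concern.** Two sources of information about the secondary pain contrasts are left unused by default. One is each patient's own baseline score. The other is the scores at neighbouring times, which carry information about a missing 18 h value. The t-test at 18 h discards every patient without an 18 h score, and the protocol's own rules make such gaps likely. The t-test comparison is also unbiased only if those gaps are unrelated to pain, whereas the mixed model needs the weaker condition that they are unrelated once the observed scores are taken into account.

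The model that would recover this information is already in the plan, but it depends on a word with no threshold. Two analysts could look at the same missingness pattern and choose differently. What is at stake is the precision and predictability of the secondary pain results, not the validity of the primary conclusion.

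**Working it through.** **Inputs.** From Power Analysis: SD 2.0, margin ±1, significance level 0.05, power 80%, 69 evaluable and 80 recruited per arm. Assumed here: SD 2.0 at every NRS time (the plan gives one SD and no time point for it), true difference 0, the correlations and missing fractions shown below, and missingness at random.

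**1. The plan's own figure.** For two one-sided tests with true difference 0, n = 2 × [SD × (z₀.₉₅ + z₀.₉₀) / margin]² = 2 × [2.0 × (1.645 + 1.282) / 1]² = 68.5, so 69 per arm. This reproduces the plan. Testing at 0.025 per side would give 85, so 69 corresponds to a 90% CI inside ±1. Exact t-based power at 69 is 79.9%.

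**2. Yardstick.** I use the chance that a 90% CI is *not* wholly inside ±1 when the arms are identical, and call this inconclusive. It is a convenient scale for precision; the plan does not set it as a rule for the secondary endpoints.

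**3. Complete data, baseline adjustment.** If baseline correlates r with the outcome, the residual SD is 2.0 × √(1 − r²). Exact t-based calculation, 69 per arm:

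| r (assumed) | Residual SD | Inconclusive |
|---|---|---|
| 0 (plan's t-test) | 2.00 | 20% |
| 0.2 | 1.96 | 18% |
| 0.4 | 1.83 | 12% |
| 0.5 | 1.73 | 8% |

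**4. At 18 h with 30% missing at random (normal approximation).** SE = 2.0 × √(2f/69), where f is the variance inflation, and inconclusive = 2 − 2Φ(1/SE − 1.645).

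- *t-test:* f = 1/0.7 = 1.429, SE = 0.407, inconclusive 42%.
- *Mixed model:* with equal within-patient correlation ρ, the other three times explain R² = 3ρ²/(1 + 2ρ) of the 18 h variance, and f = (1 − R²)/0.7 + R². For ρ = 0.5: R² = 0.375, f = 0.893 + 0.375 = 1.268, SE = 0.383, inconclusive 34%.
- *Mixed model with baseline:* replace ρ by ρ′ = (ρ − r²)/(1 − r²) and multiply f by (1 − r²). For ρ = 0.5, r = 0.4: ρ′ = 0.405, R² = 0.272, f = 0.84 × 1.312 = 1.102, SE = 0.357, inconclusive 25%.

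| ρ, r (assumed) | t-test | Mixed model | With baseline |
|---|---|---|---|
| 0.3, 0.2 | 42% | 38% | 36% |
| 0.5, 0.4 | 42% | 34% | 25% |
| 0.7, 0.5 | 42% | 28% | 15% |

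The two correlations move together here, so the last column is a range over paired assumptions.

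**5. Less missingness.** By the same formulas, unadjusted: at 20% missing, 33% by t-test against 25–30% by mixed model; at 10% missing, 25% against 22–24%.

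**6. The 6 h primary.** With complete 6 h data the unadjusted random-intercept model gave the same 6 h estimate as the t-test difference in simulation (69 per arm, ρ = 0.5, 18 h scores 30% or 50% missing, 120 runs each). Its standard error was on average within about 0.5% of the t-test's.

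**The case against.** The strongest reply is that these endpoints are secondary and unpowered, that t-tests with confidence intervals are conventional for them, and that the plan already names a mixed model for missing data. The gain also rests on assumed correlations and an assumed missing fraction. It is small if missingness is light or baseline predicts little. Baseline adjustment is a design choice, not the repair of an error. All of this stands, and it limits the weight of the point. It does not remove the case for a more precise method that uses data already collected.

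A reader might infer more than the documents support:

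- *That the primary conclusion is exposed to the mixed model.* Data Analysis assigns the two one-sided tests without condition, and Baseline data collection says all patients are still admitted at 6 h.
- *That the unstated CI level undermines the sample size.* The interval accompanies the test ("We will also calculate a point and confidence interval estimate of the difference between LPB and PENG groups"), and 69 per arm reproduces only with 0.05 per one-sided test, so a 90% CI can be inferred. Stating it is a wording matter.
- *That the trigger lets analysts choose a method after seeing results by arm.* It concerns missingness, and the Measurements section has the data analysed by personnel blinded to allocation. The undefined word is a minor gap.
- *That ±1 binds all eight NRS endpoints.* The hypothesis is broad ("We hypothesize that the PENG block will provide equivalent analgesia to LPB after THA"), and one sentence is general ("We define an equivalent mean pain score to be a margin of one point in either direction on the eleven-point NRS scale"). But in the Objectives the definition follows directly on the primary outcome, the power calculation ends at 6 h movement pain, and the two one-sided tests are given to that endpoint alone. The natural reading ties the margin to the primary.
- *That a non-significant secondary difference will be called equivalent.* The plan does not propose this.

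**Conclusion.** The point holds as an improvement to the analysis of the secondary pain endpoints. With complete data, adjusting for baseline cuts the chance of an inconclusive result from 20% to between 18% and 8%. At 18 h with 30% missing, the unadjusted model cuts it from 42% to 28–38%, and the baseline-adjusted model to 15–36%.

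These sizes depend on SD 2.0 at every time, 69 per arm, identical arms, baseline correlations of 0.2 to 0.5, within-patient correlations of 0.3 to 0.7, and missingness at random. The documents give none of the correlations and no expected missing fraction. Sleep may be related to pain, so missingness at random at 18 h is itself uncertain. The primary test, the sample size and the non-NRS secondary outcomes are unaffected.

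**What to change.** 1. Drop the *substantial* trigger. Always fit an arm-by-time mixed model to the movement series and another to the rest series, each adjusted for the matching baseline NRS, as the analysis of the seven secondary pain endpoints.
2. State that the 6 h movement-pain conclusion rests on the two one-sided t-tests at 0.05 each, equivalently the 90% CI within ±1, whatever the missingness.
3. Show the secondary contrasts with 90% CIs beside the ±1 margin as a supportive display only, and state that a non-significant difference will not be read as equivalence.
4. Report missing 18 h scores by arm and reason (asleep, or awake without movement), because the model relies on missingness at random.

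**Cost.** A few sentences in the analysis section and a few lines of R, with no new data or patients. Letting the variance differ by time would be a reasonable refinement but may need a package other than lme4. The visible downside is that some secondary results will be shown as inconclusive. Without adjustment this is about 20% each at SD 2.0 with complete data and identical arms, and 49% if the SD were 2.5 (assumed).
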